**Table 5. Differentiating DIKI and DICI in Pediatric Participants**

|               | AKI (including DIKI)
Any one of the below  | DICI  |
|---------------|---|---|
| Scys & Screat | Simultaneous, confirmed Scys increase of $\geq 0.3$ mg/L and confirmed Screat increase of $\geq 0.3$ mg/dL post-baseline.         | Confirmed Screat increase of $\geq 0.3$ mg/dL post-baseline without simultaneous confirmed increase of $\geq 0.3$ mg/L in Scys post-baseline. |
| Albuminuria   | Confirmed albuminuria increase (see Appendix 6 , Section 10.6 , for Grades A1 to A3 quantitation) | No albuminuria increase   |
| Urine volume  | Urine volume $<0.5$ mL/kg/h for 6 consecutive hours (if monitored)  | No urine volume decrease  |

Regardless of the presence or absence of increase in Screat, DIKI and other causes of AKI may be suspected if either there is (i) new-onset or worsening albuminuria or proteinuria are detected or (ii) urine volume (if measured) is  $<0.5$  mL/kg/h for 6 consecutive hours.

#### Follow-up Assessments

The participant should return to the site for evaluation as soon as possible, preferably within 48 hours of awareness of the abnormal renal function result. Evaluation should include physical examination, laboratory tests, detailed medical and surgical history, review of all medications (including recreational drugs and supplements [herbal]), family history, sexual history, travel history, blood transfusion, and potential occupational exposure to chemicals. If appropriate, nephrology consultation may be recommended to facilitate differentiation of renal parenchymal disease, pre-renal azotemia, and post-renal obstruction. All confirmed cases of clinically relevant decrease in kidney function should be considered potential cases of DIKI if no other reason for the kidney function abnormalities has been found.

Laboratory assessments should include simultaneous serum cystatin C (Scys) and serum creatinine (Screat) tests. Renal function should be evaluated using the appropriate equation or creatinine reference values described in [Appendix 6](#) (Section [10.6](#)). Assessments of urine albumin-to-creatinine ratio or urine volume may also be performed as appropriate.

#### 7.1.2. Liver Injury

A participant who meets the criteria of potential DILI (Hy's law) case as described in [Appendix 5](#) in Section [10.5](#) or if they meet either of the below criteria, will be withdrawn from study intervention.

- Participants >30 days old with finding of pre-dose AST, ALT or T bili >2 × ULN;
- Any participant during study intervention with at least 2 of the following labs AST, ALT or T bili increase by >2 ULN.

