##### **Medical Conditions:**

1. Any medical, developmental, or behavioral condition (including history of self-harmful behaviors) or laboratory abnormality that may increase the risk of study participation or, in the investigator's judgment, make the participant inappropriate for the study.
2. Premature infants (gestational age less than 35 weeks) AND <1 year of post-natal age.  
Note: Infants 35- and 36-week gestational age are permitted if they weigh at least 2.5 kg and are at least 2 months post-natal age.
3. **CCI** [REDACTED] with intrauterine growth restriction defined by having 3 or more of the following:
  - Birth weight <10th percentile on population-based or customized growth charts
  - Head circumference <10th percentile
  - Length <10th percentile
  - Prenatal diagnosis of fetal growth restriction
  - Maternal pregnancy information associated with fetal growth restriction (eg, hypertension, pre-eclampsia)
4. Any clinically significant ECG abnormality in a participant's medical history, or in the pre-dose ECG that per investigator judgement may affect participant safety or interpretation of study results. Note: If sinus tachycardia is present, and not worse than expected due to underlying disease, participant may be considered at investigator discretion, if the sinus tachycardia is not expected to interfere with evaluation of response to study intervention.
5. Known history of hepatic disease, concern for active acute or chronic viral hepatitis, or acute hepatic failure.

6. Participants >~~CC1~~ days only: Known history of AST, ALT, or T bili abnormalities  $>2 \times$  ULN within 6 months of screening. Laboratory assessments not required at screening for participants >~~CC1~~ days unless deemed necessary by the investigator to confirm normal hepatic function. Note: Participants with history of elevated bilirubin due to neonatal hyperbilirubinemia that is resolved with T Bili values within reference range may be enrolled.
7. History of epilepsy or seizures. Participants with a history of febrile seizures will be permitted to enroll.
8. Expected to receive or has received an antiviral for another respiratory viral infection (eg, influenza or COVID-19) within 10 days of screening.

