**Diagnostic Assessments**

19. Baseline 12-lead ECG with QTcF  $\geq$ 450 ms.
20. **CCI** old) with any of the following laboratory abnormalities at screening:
  - Total bilirubin  $>2 \times$  ULN
  - AST  $>2 \times$  ULN
  - ALT  $>2 \times$  ULN

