#### 10.5. Appendix 5: Liver Safety: Suggested Actions and Follow-Up Assessments

The threshold of laboratory abnormalities for a potential Drug-Induced Liver Injury (DILI) case depends on the participant's individual baseline values and underlying conditions. Participants who present with the following laboratory abnormalities should be evaluated further as potential DILI (Hy's law) cases to definitively determine the etiology of the abnormal laboratory values:

Parameters for pediatric hepatic dysfunction can be defined as at least 2 of the below:

- Total bilirubin  $>2 \times$  ULN
- AST  $>2 \times$  ULN
- ALT  $>2 \times$  ULN

The participant should return to the investigator site and be evaluated as soon as possible, preferably within 48 hours from awareness of the abnormal results. This evaluation should include laboratory tests, detailed history, and physical assessment.

In addition to repeating measurements of AST and ALT and T bili for suspected Hy's law cases, additional laboratory tests should include albumin, CK, direct and indirect bilirubin, GGT, PT/INR, eosinophil (%), and alkaline phosphatase. Consideration should also be given to drawing a separate tube of clotted blood and an anticoagulated tube of blood for further testing, as needed, for further contemporaneous analyses at the time of the recognized initial abnormalities to determine etiology. A detailed history, including relevant information, including factors outlined in the list below, should be collected as applicable.

- Signs and symptoms of hepatotoxicity (nausea, vomiting, fatigue, jaundice, RUQ pain)
- review of ethanol use and consumption
- acetaminophen/paracetamol (either by itself or as a coformulated product in prescription or over the counter medications)
- recreational drug use
- supplement (herbal) use and consumption
- family history
- sexual history
- travel history
- history of contact with a jaundiced person

- surgery
- blood transfusion
- history of liver or allergic disease
- potential occupational exposure to chemicals
- environmental exposures
- household/living arrangements

Further testing for acute hepatitis A, B, C, D, and E infection, total bile acids, liver imaging (eg, biliary tract), and collection of serum samples for acetaminophen/paracetamol drug and/or protein adduct levels may be warranted.

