All cases demonstrated on repeat testing as meeting the laboratory criteria of AST/ALT and T bili elevation defined above should be considered potential DILI (Hy's law) cases if no other reason for the liver enzyme abnormalities has yet been found. Such potential DILI (Hy's law) cases are to be reported as SAEs, irrespective of availability of all the results of the investigations performed to determine etiology of the liver enzyme abnormalities.

The preferred tube is the red top tube for liver transaminases (ALT/AST), bilirubin and alkaline phosphatase. For additional information regarding the proper pediatric tubes for these labs, please contact your central lab.

In certain diseases such as rare diseases (eg, Duchenne Muscular Dystrophy) there could be an adjustment to the liver enzyme parameters to account for the increased baseline of the participant entering the clinical trial. Please note hepatic labs reference ranges may differ for adult and pediatric population, certain diseases and lab performing the test.

For additional information regarding DILI please see Guidance for Industry (fda.gov).

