### Potential Cases of Drug Induced Liver Injury

Humans exposed to a drug who show no sign of liver injury (as determined by elevations in transaminases) are termed "tolerators," while those who show transient liver injury but adapt are termed "adaptors." In some participants, transaminase elevations are a harbinger of a more serious potential outcome. These participants fail to adapt and therefore are "susceptible" to progressive and serious liver injury, commonly referred to as DILI. Participants who experience a transaminase elevation above  $3 \times$  ULN should be monitored more frequently to determine if they are "adaptors" or are "susceptible."

In the majority of DILI cases, elevations in AST and/or ALT precede T bili elevations ( $>2 \times$  ULN) by several days or weeks. The increase in T bili typically occurs while AST/ALT is/are still elevated above  $3 \times$  ULN (ie, AST/ALT and T bili values will be elevated within the same laboratory sample). In rare instances, by the time T bili elevations are detected, AST/ALT values might have decreased. This occurrence is still regarded as a potential DILI. Therefore, abnormal elevations in either AST OR ALT in addition to T bili that meet the criteria outlined

PFIZER CONFIDENTIAL

below are considered potential DILI (assessed per Hy's law criteria) cases and should always be considered important medical events, even before all other possible causes of liver injury have been excluded.

The threshold of laboratory abnormalities for a potential DILI case depends on the participant's individual baseline values and underlying conditions. Participants who present with the following laboratory abnormalities should be evaluated further as potential DILI (Hy's law) cases to definitively determine the etiology of the abnormal laboratory values:

- Participants with AST/ALT and T bili baseline values within the normal range who subsequently present with AST OR ALT values  $\geq 3 \times$  ULN AND a T bili value  $\geq 2 \times$  ULN with no evidence of hemolysis and an alkaline phosphatase value  $< 2 \times$  ULN or not available.
- For participants with baseline AST OR ALT OR T bili values above the ULN, the following threshold values are used in the definition mentioned above, as needed, depending on which values are above the ULN at baseline:

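### The on-treatment liver withdrawal bullet in Protocol 7.1.2 reads as a rise of more than 2 x ULN, where every matching threshold is a value above 2 x ULN

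*Protocol*

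**What the plan says.** Protocol 7.1.2 gives three alternative routes to mandatory withdrawal from study intervention, joined by *or*:

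- meeting the potential DILI (Hy's law) criteria in Appendix 5 (Section 10.5);
- a pre-dose rule: "Participants >30 days old with finding of pre-dose AST, ALT or T bili >2 × ULN";
- an on-treatment rule: "Any participant during study intervention with at least 2 of the following labs AST, ALT or T bili increase by >2 ULN".

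The last bullet has no multiplication sign and names no reference value.

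The related thresholds elsewhere are values above 2 x ULN. Exclusion 6 in Section 5.2 ("Known history of AST, ALT, or T bili abnormalities") uses it for results within 6 months of screening. Exclusion 20 ("with any of the following laboratory abnormalities at screening") applies it separately to bilirubin, AST and ALT.

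Appendix 5 has two lists. The first, "Parameters for pediatric hepatic dysfunction can be defined as at least 2 of the below", counts T bili, AST and ALT each above 2 x ULN and does not require bilirubin. It is introduced as identifying children to be evaluated further as potential DILI cases. The text that follows it speaks of "All cases demonstrated on repeat testing as meeting the laboratory criteria of AST/ALT and T bili elevation defined above", to be considered potential DILI "if no other reason for the liver enzyme abnormalities has yet been found". The second list starts from "Participants with AST/ALT and T bili baseline values within the normal range who subsequently present with AST OR ALT values" of at least 3 x ULN and also requires T bili of at least 2 x ULN, with adjusted thresholds for raised baselines. No sentence says which list 7.1.2 refers to.

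**The concern.** An increase by an amount is a change from some starting point, and on treatment the natural starting point is baseline. A site taking the bullet at its word would subtract baseline before comparing with 2 x ULN. A site taking it as a slip for *increase to* would compare the value itself. The two sites could then make different mandatory withdrawal decisions for the same child.

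The difference grows with baseline, so under the literal reading the children who start highest are withdrawn latest. Raised baselines are possible: the pre-dose bullet and exclusion 20 act only above 2 x ULN, so a child at 1 to 2 x ULN can be dosed. Section 2.3.1 lists hepatobiliary effects as a potential risk and reports mild transient enzyme elevations in completed studies.

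**Working it through.** The plan states no figure to reproduce here. The check compares the triggers in multiples of ULN. Baselines are assumed for illustration.

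**Inputs.** The factor 2 and the two-of-three count come from 7.1.2 and the first Appendix 5 list. The second-list thresholds (AST or ALT at least 3, T bili at least 2, for normal baselines) come from the Appendix 5 part headed Potential Cases of Drug Induced Liver Injury. For AST or ALT already above normal, that part requires at least twice baseline and at least 3, or at least 8, whichever is smaller.

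**Trigger for one test with baseline b and on-treatment value v.**

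- Value reading: v > 2.
- Rise reading: v − b > 2, that is v > b + 2.
- The readings disagree for v above 2 and up to b + 2, a band of width b.

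| Baseline | Value reading | Rise reading | Width of band |
|---|---|---|---|
| 0.5 | >2.0 | >2.5 | 0.5 |
| 0.8 | >2.0 | >2.8 | 0.8 |
| 1.0 | >2.0 | >3.0 | 1.0 |
| 1.5 | >2.0 | >3.5 | 1.5 |
| 1.8 | >2.0 | >3.8 | 1.8 |
| 2.0 | >2.0 | >4.0 | 2.0 |

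**Direction.** Since b cannot be negative, v − b > 2 implies v > 2. Any child who meets the rise reading on two tests therefore also meets the value reading on those two tests. The rise reading can only be more lenient.

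**Specific patterns, AST and ALT equal, T bili 0.5.**

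| AST and ALT | Baseline | Rise | Value reading | Rise reading | Pediatric list | AST/ALT plus T bili raised | Second list |
|---|---|---|---|---|---|---|---|
| 2.6 | 0.8 | 1.8 | withdraw | no | met | no | no |
| 2.9 | 1.0 | 1.9 | withdraw | no | met | no | no |
| 3.7 | 1.8 | 1.9 | withdraw | no | met | no | no |
| 3.2 | 0.8 | 2.4 | withdraw | withdraw | met | no | no |

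The pediatric-list column decides the consequence. Any child on whom the two readings disagree has at least two tests above 2 x ULN, because that is what the value reading requires, and so meets the pediatric list. The wording of the bullet changes the outcome only if meeting that list is not enough to be a potential DILI case for 7.1.2.

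**Is it enough?** The texts point both ways.

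- For: the list is introduced as describing potential DILI cases, it is the only one labelled pediatric, and 7.1.2 asks for no repeat test before withdrawal.
- Against: the introduction asks for evaluation. The paragraph that goes on to call cases potential DILI refers to repeat testing and to AST/ALT *and* T bili elevation. The second list requires bilirubin outright. AST plus ALT with normal bilirubin meets neither of those.

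**The case against.** The strongest reply is that the *or* in 7.1.2 already covers the case. AST and ALT above 2 x ULN meet the pediatric list, so the child is withdrawn through the Appendix 5 route whatever the bullet means. The closing paragraph on repeat testing leads to SAE reporting and does not mention withdrawal, so it need not restrict that route. This is a fair reading, and if it is right the literal bullet is redundant and harmless. It stands as one of two open readings, because Appendix 5 does not settle the question.

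A second reply is that the protocol names baseline when it means change, as in the QTcF rule in 7.1.3 and the bilirubin adjustment in Appendix 5, and this bullet does not. That supports the value reading as the intent. It does not remove the ambiguity: the creatinine rules in 7.1.1 use increase for a genuine rise, and one of them names no baseline.

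Third, the practical room is small. The course is 5 or 6 days, and Protocol Table 7 budgets two chemistry draws after screening. Section 7.1 allows discontinuation for any condition posing a risk, Appendix 5 asks for closer monitoring above 3 x ULN, and 4.1.1 has a laboratory interruption rule. These limit the harm, but they rest on judgement, fall short of withdrawal, or need two or more participants.

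A reader might infer that this bullet is the only mandatory route for raised transaminases with normal bilirubin, so that such children would certainly stay on drug. The documents do not support that, because the pediatric list may itself be such a route. Nor do they support counting doses given while a repeat test is awaited: 7.1.2 makes no repeat test a condition of withdrawal, and the visit days are redacted.

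**Conclusion.** The point holds as a defect of wording in a mandatory safety rule. The on-treatment bullet is out of line with its sibling bullet, exclusions 6 and 20 and the pediatric list, and a value above 2 x ULN is probably what was intended. Taken literally, the trigger moves up by exactly the child's baseline: 0.8 x ULN at baseline 0.8, and 1.8 x ULN at baseline 1.8.

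That the wording is inconsistent is certain. That withdrawal would be delayed is conditional: it needs a site to read the bullet as a rise and also to read the pediatric list as calling only for evaluation. Two lists under one potential DILI label might also suggest a problem with SAE reporting. Having both would at most lead to over-reporting, so no change to the SAE rules is argued for. The documents give no basis for saying how often the disputed pattern would occur, and no sample size or primary safety table depends on it.

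**What to change.** Reword the second bullet of 7.1.2 so that withdrawal applies when at least two of AST, ALT and T bili are >2 x ULN. Add one sentence, in 7.1.2 or Appendix 5, stating that meeting the pediatric two-of-three list is sufficient for withdrawal under 7.1.2. A clarification letter or amendment can carry both, and no new procedure or blood draw is needed.

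If dosing has ended, list in the study report any child with at least two of the three tests above 2 x ULN on treatment who was not withdrawn.

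The cost is possibly a few more withdrawals for milder elevations.

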#### 7.1.3. ECG Changes

A participant who meets either bulleted criterion will be withdrawn from the study intervention.

- QTcF >500 ms.
- Change from baseline: QTcF  $\geq$  60 ms

If a clinically significant finding is identified (including, but not limited to, changes from baseline in QTcF after enrollment), the investigator or qualified designee will determine if the participant can continue in the study and if any change in participant management is needed. This review of the ECG printed at the time of collection must be documented. Any new clinically relevant finding should be reported as an AE.

#### 7.1.4. COVID-19

If a participant has COVID-19 during the study, this should be reported as an AE or SAE (as appropriate) and appropriate medical intervention provided.

Study treatment may continue unless the investigator/treating physician is concerned about the safety of the participant, or if the participant will be started on an antiviral, in which case study intervention should be discontinued.

It is recommended that the investigator discuss temporary or permanent discontinuation of study intervention with the study medical monitor.

### 7.2. Participant Discontinuation/Withdrawal From the Study

A participant may withdraw from the study at any time at their own request, or at the request of the parent(s)/legal guardian. Reasons for discontinuation from the study include the following:

- Refused further study procedures;
- Lost to follow up;
- Death;
- Investigator decision;
- Study terminated by sponsor;

- Withdrawal of consent/assent by parent(s)/legal guardian or by a child who has provided assent during any phase of the study

At the time of discontinuing from the study, if possible, an early discontinuation visit should be conducted. See the [SoA](#) for assessments to be collected at the time of study discontinuation and follow-up and for any further evaluations that need to be completed.

The early discontinuation visit applies only to participants who are enrolled/randomized and then are prematurely withdrawn from the study. Participants/participant's parent(s)/legal guardian should be questioned regarding their reason for withdrawal.

The participant will be permanently discontinued from the study intervention and the study at that time.

If a participant/participant's parent(s)/legal guardian withdraws from the study, they may request destruction of any remaining samples taken and not tested, and the investigator must document any such requests in the site study records and notify the sponsor accordingly.

If the participant withdraws from the study and also withdraws assent (see Section 7.2.1) for disclosure of future information, no further evaluations will be performed, and no additional data will be collected. The sponsor may retain and continue to use any data collected before such withdrawal of assent.

#### **7.2.1. Withdrawal of Consent**

Participants/participant's parent(s)/legal guardian who request to discontinue receipt of study intervention will remain in the study and must continue to be followed for protocol-specified follow-up procedures. The only exception to this is when a participant's parent(s)/legal guardian specifically withdraws consent/assent for any further contact with them or persons previously authorized by the participant's parent(s)/legal guardian to provide this information. Parent(s)/legal guardian s should notify the investigator in writing of the decision to withdraw consent from future follow-up, whenever possible. The withdrawal of consent should be explained in detail in the medical records by the investigator, as to whether the withdrawal is only from further receipt of study intervention or also from study procedures and/or posttreatment study follow up and entered on the appropriate CRF page. In the event that vital status (whether the participant is alive or dead) is being measured, publicly available information should be used to determine vital status only as appropriately directed in accordance with local law.

#### **7.3. Lost to Follow-Up**

A participant will be considered lost to follow-up if the participant/ participant's parent(s)/legal guardian repeatedly fails to return for scheduled visits and is unable to be contacted by the study site.

The following actions must be taken if a participant/ participant's parent(s)/legal guardian fails to attend a required study visit:

- The site must attempt to contact the participant's parent(s)/legal guardian and reschedule the missed visit as soon as possible. Counsel the participant's parent(s)/legal guardian on the importance of maintaining the assigned visit schedule, and ascertain whether the participant's parent(s)/legal guardian wishes to and/or should continue in the study;
- Before a participant is deemed lost to follow-up, the investigator or designee must make every effort to regain contact with the participant's parent(s)/legal guardian (where possible, 3 telephone calls and, if necessary, a certified letter to the participant's parent(s)/legal guardian's last known mailing address or local equivalent methods). These contact attempts should be documented in the participant's medical record;
- Should the participant's parent(s)/legal guardian continue to be unreachable, the participant will be considered to have withdrawn from the study.

Participants may be replaced at Sponsor discretion as described in Section [4.1](#) and Section [9.5](#).

